Statistical Analysis Plan

A Pilot Study to Assess WATCHMAN FLX™ Pro Implants by Cardiac Computed Tomography, Magnetic Resonance Imaging and Transesophageal Echocardiography: WATCHMAN FLX™ Pro CT

WATCHMAN FLX™ Pro CT

S2517

CLINICAL INVESTIGATION PLAN

National Clinical Trial (NCT) Identifier Number: NCT05567172

CONFIDENTIAL

DO NOT COPY OR DISTRIBUTE WITHOUT WRITTEN PERMISSION

Revision History

[figure not shown]
Revision Number	Protocol Version	Date
A	92929614 Rev/Ver C	27-Mar-2023

2. Protocol Synopsis

A Pilot Study to Assess WATCHMAN FLX™ Pro Implants by Cardiac Computed Tomography, Magnetic Resonance Imaging and Transesophageal Echocardiography: WATCHMAN FLX™ Pro CT

Study Objective(s)	The primary objective of this study is to measure device tissue coverage post-implantation of the WATCHMAN FLX™ Pro Left Atrial Appendage Closure (LAAC) Device (WATCHMAN FLX Pro) using the serial advanced imaging modalities of cardiac computed tomography (CT) and transesophageal echocardiography (TEE) and assess its relationship, if any, to clinical events.
Planned Indication(s) for Use	As per the clinical Instructions for Use (IFU), WATCHMAN FLX Pro is intended to prevent thrombus embolization from the left atrial appendage and reduce the risk of life-threatening bleeding events in patients with non-valvular atrial fibrillation who are eligible for anticoagulation therapy or who have a contraindication to anticoagulation therapy.
Investigational Devices and Sizes	Investigational devices include the WATCHMAN FLX™ Pro Left Atrial Appendage Closure Device sizes 20mm, 24mm, 27mm, 31mm, 35mm and 40mm Note 1: The WATCHMAN FLX Pro LAAC Device comes preloaded on the WATCHMAN FLX Pro Delivery Catheter. The preloaded delivery system is used in conjunction with any commercially available WATCHMAN® Access System (access sheath and dilator).
Study Design	WATCHMAN FLX™ Pro CT is a prospective, single-arm, single-center, premarket investigation to assess device tissue coverage in subjects with non-valvular atrial fibrillation (AF) who receive the WATCHMAN FLX Pro device to reduce the risk of stroke. Serial advanced imaging modalities such as CT and TEE will be used. A core laboratory will independently assess select results. A subject is considered enrolled in the study when the subject or the subject's legally authorized representative signs an Informed Consent Form (ICF) approved by the Independent Ethics Committee (IEC). Up to 25 subjects in whom placement of a WATCHMAN FLX Pro device is attempted will be enrolled. A baseline assessment including TEE and/or CT imaging with optional cardiac magnetic resonance imaging (MRI) will be done within 14 days prior to the implant procedure following core

A Pilot Study to Assess WATCHMAN FLX™ Pro Implants by Cardiac Computed Tomography, Magnetic Resonance Imaging and Transesophageal Echocardiography: WATCHMAN FLX™ Pro CT

	
laboratory guidelines. Follow-up clinical assessment and imaging will occur at 14 days, 45 days, and 3 months post implant procedure; only clinical assessment will be required at 12 months (unless an in-person assessment is required based on other data). Subjects who are enrolled but not implanted with a WATCHMAN FLX Pro LAAC device will be followed for safety through 12 months after the initial attempted implant procedure by telephone or review of clinical files but will not undergo imaging assessments or evaluation of biochemical markers including measures of coagulation, platelet and endothelial activation and inflammation.
 
The study design is summarized below.
  
Eligibility Assessment Informed Consent Subject signs ICF^a Subject meets study clinical inclusion and exclusion criteria (based on standard of care assessments) Baseline Clinical Assessment Subject Enrollment* Index Procedure PP/PD^b 14d 45d 3m 1y Follow-up^c In-person Telephone
 
^a Subjects must sign the study ICF before any study-specific assessments can be carried out. ^b Subjects who provide informed consent are considered enrolled. ^c Post-procedure/Pre-discharge ^d Visits are in-person through 3 months and in-person (preferred) or via telephone interview at 1 year.
 
WATCHMAN FLX Pro CT Study Design Overview
 
Eligibility is determined per standard of care. Any additional study specific testing to verify inclusion/exclusion criteria must be done after the ICF is signed.
 
Abbreviation: ICF=Informed Consent Form

Planned Number of Subjects	Up to 25 subjects in whom placement of a WATCHMAN FLX Pro device is attempted will be enrolled.
Planned Number of Centers / Countries	There will be 1 investigational center in western Europe.
Primary Endpoint	Device surface morphology (inclusive of tissue coverage) post implant procedure as assessed over time using the serial advanced imaging modalities of cardiac computed tomography (CT) and transesophageal echocardiography (TEE) with data evaluated by an independent core laboratory.

**A Pilot Study to Assess WATCHMAN FLX™ Pro Implants by Cardiac
Computed Tomography, Magnetic Resonance Imaging and
Transesophageal Echocardiography: WATCHMAN FLX™ Pro CT**

Additional Endpoints	
Additional measurements will be collected peri- and post-procedure, predischarge, and at 14 days, 45 days, 3 months, and 12 months (if needed) after the implant procedure, unless otherwise specified below.
 
 • Safety endpoints (adjudicated by an independent Clinical Events Committee [CEC]): 
 ○ All-cause mortality (cardiovascular/unknown and non-cardiovascular) ○ Stroke (disabling and non-disabling; ischemic and hemorrhagic; see Note 2) ○ Systemic embolism ○ Bleeding: International Society on Thrombosis and Haemostasis (ISTH) major and non-major clinically significant^a 
 ▪ Procedural bleeding (≤ 7 days post-procedure) ▪ Non-procedural bleeding (> 7 days post-procedure) ○ Pericardial effusion/tamponade requiring pericardiocentesis or surgery 
Note 2: For subjects diagnosed with a neurological event (e.g., stroke, transient ischemic attack [TIA]), Modified Rankin Scale (mRS) and National Institutes of Health Stroke Scale (NIHSS) should be performed after the event. It is recommended that the subject be contacted regarding mRS assessment at 90 ± 14 days following any suspected stroke; the simplified mRS questionnaire^b may be used for this follow-up assessment. It is also recommended that imaging be performed after the event to screen for device related thrombus. If performed, imaging results should be sent to the core laboratory.
 
 • Device Success: defined as implantation of a WATCHMAN FLX Pro device without in-hospital mortality • Assessments by serial imaging modalities (CT and TEE; cardiac MRI optional) at 14 days, 45 days, and 3 months; data will be evaluated by an independent core lab 
 ○ Device seal post implant procedure (see Note 3 and Note 4) ○ Device-related thrombus (including hypoattenuated thickening [HAT] per CT analysis)
-----------------------------	--

A Pilot Study to Assess WATCHMAN FLX™ Pro Implants by Cardiac Computed Tomography, Magnetic Resonance Imaging and Transesophageal Echocardiography: WATCHMAN FLX™ Pro CT

	
Note 3: Results are classified as no leak, leak >0 and $\leq 5\text{mm}$, or leak $>5\text{mm}$.
 
Note 4: TEE is required at 12 months if the 3-month TEE assessment suggests a leak $> 5\text{mm}$ or the 3-month CT assessment suggests a leak $> 3\text{mm}$; results must be sent to the core laboratory.
 
• 4D cardiac MRI flow analysis (if available) of the left atrium (LA) and LAA before and serially after device implant at 14 days, 45 days, and 3 months; data will be evaluated by an independent core lab• Changes compared to baseline in measures of biochemical markers including coagulation, platelet and endothelial activation and inflammation at 14 days, 45 days, and 3 months post implant procedure; correlations with morphological findings from imaging assessment of the device surface will be examined
a: Schulman S and Kearon C. J Thromb Haemost 2005;3:692-694Kaatz S, et al. J Thromb Haemost 2015;13:2119-26b: Bruno A, et al. Stroke 2011;42:2276-2279
Follow-up Schedule	Follow-up for all subjects will occur post-implant on the procedure day, at predischarge, and at 14 days, 45 days, 3 months, and 12 months post implant procedure. Follow-up will include clinical assessments at all time points and imaging assessments at 14 days, 45 days, and 3 months. Subjects who are enrolled but not implanted with a WATCHMAN FLX Pro device in the correct position will be followed for safety through 12 months after the initial attempted implant procedure by telephone or review of clinical files but will not undergo imaging assessments or evaluation of biochemical markers including measures of coagulation, platelet and endothelial activation and inflammation. The study will be considered complete after all available subjects have finished the 12-month follow-up visit.
Study Duration	Subjects will be followed for 12 months after the implant procedure. Enrollment is expected to take minimally 5 months; therefore, the total study duration from first subject enrolled to last subject follow-up is estimated to be at least 17 months.

A Pilot Study to Assess WATCHMAN FLX™ Pro Implants by Cardiac Computed Tomography, Magnetic Resonance Imaging and Transesophageal Echocardiography: WATCHMAN FLX™ Pro CT

Inclusion Criteria	
Inclusion criteria are listed below.
 
IC1. Subject is of legal age to participate in the study per the laws of their respective geography.
 
IC2. Subject has documented non-valvular atrial fibrillation (i.e., atrial fibrillation in the absence of moderate or greater mitral stenosis or a mechanical heart valve) and who has a relative or absolute contraindication to anticoagulation.
 
IC3. Subject is deemed suitable for the protocol-defined pharmacologic regimen.
 
IC4. Subject or legal representative is able to understand and willing to provide written informed consent to participate in the study.
 
IC5. Subject is able and willing to return for required follow-up visits and examinations.

Exclusion Criteria	
Exclusion criteria are listed below.
 
EC1. Subject is currently enrolled in another investigational study, except if the subject is participating in a mandatory governmental registry, or a purely observational registry with no associated treatment.
 
EC2. Subject has eGFR <30 mL/min (chronic kidney disease stage IV or stage V).
 
EC3. Subject is contraindicated for TEE.
 
EC4. Subject requires long-term anticoagulation therapy for reasons other than AF-related stroke risk reduction (e.g., due to an underlying hypercoagulable state).
 
EC5. Subject had or is planning to have any cardiac or non-cardiac intervention or surgical procedure within 30 days prior to or 60 days after implant (including, but not limited to, cardioversion, percutaneous coronary intervention, cardiac ablation, cataract surgery, etc.).
 
EC6. Subject had a prior stroke (of any cause, whether ischemic or hemorrhagic) or TIA within the 30 days prior to enrollment.
 
EC7. Subject had a prior major bleeding event per ISTH definitions within the 30 days prior to enrollment. Lack of resolution of related clinical sequelae or planned and pending interventions to resolve bleeding/bleeding source are a further exclusion regardless of timing of the bleeding event.

**A Pilot Study to Assess WATCHMAN FLX™ Pro Implants by Cardiac
Computed Tomography, Magnetic Resonance Imaging and
Transesophageal Echocardiography: WATCHMAN FLX™ Pro CT**

	
EC8. Subject has an active bleed.
 
EC9. Subject has a reversible cause for AF or has transient AF.
 
EC10. Subject has no LAA or the LAA is surgically ligated.
 
EC11. Subject has had a myocardial infarction (MI) documented in the clinical record as either a non-ST elevation MI (NSTEMI) or as an ST-elevation MI (STEMI), with or without intervention, within 30 days prior to enrollment.
 
EC12. Subject has a history of atrial septal repair or has an atrial septal defect/patent foramen ovale (ASD/PFO) device.
 
EC13. Subject has a known contraindication to percutaneous catheterization procedure.
 
EC14. Subject has a cardiac tumor.
 
EC15. Subject has signs/symptoms of acute or chronic pericarditis.
 
EC16. Subject has an active infection.
 
EC17. There is evidence of tamponade physiology.
 
EC18. Subject has New York Heart Association Class IV congestive heart failure at the time of enrollment.
 
EC19. Subject is of childbearing potential and is, or plans to become, pregnant during the time of the study (method of assessment per study physician's discretion).
 
EC20. Subject has a documented life expectancy of less than 6 months.

Adjunctive Pharmacologic Therapy	Subjects must be treated with single antiplatelet therapy (SAPT; aspirin or P2Y ₁₂ inhibitor) for at least 3 months following WATCHMAN FLX Pro implantation.
Multiple Interventions During Index Procedure	No concomitant procedures are to be performed at the time of the WATCHMAN FLX Pro implant procedure with the exception of implantable loop recorder implants/explants. This includes, but is not limited to, cardiac ablation procedures, transcutaneous valve procedures, cardioversions, coronary stent implantation, pacemaker or implantable cardioverter defibrillator generator change, etc.
Statistical Methods	
Analysis Sets	Analysis sets are listed below.

**A Pilot Study to Assess WATCHMAN FLX™ Pro Implants by Cardiac
Computed Tomography, Magnetic Resonance Imaging and
Transesophageal Echocardiography: WATCHMAN FLX™ Pro CT**

	
- Intention-To-Treat (ITT): This population includes all subjects who sign an ICF and are enrolled in the study, regardless of whether the study device is implanted.- Implanted: This population includes all subjects who sign an ICF, are enrolled in the study, and are successfully implanted with the study device in the correct position.
Statistical Hypothesis	There is no formal statistical hypothesis for this observational, single-arm study. No statistical inference will be made in the study.
Methods	Outcomes in the overall treatment cohort will be summarized using descriptive statistics for continuous variables (mean, standard deviation, number of observations, minimum and maximum) and discrete variables (percentage and count/sample).

3. Table of Contents

1. TITLE PAGE	1
2. PROTOCOL SYNOPSIS.....	2
3. TABLE OF CONTENTS.....	9
3.1. Table of Figures.....	10
3.2. Table of Tables	10
4. INTRODUCTION	11
5. STUDY OBJECTIVES AND ENDPOINTS.....	11
5.1. Study Objectives.....	11
5.2. Study Endpoints	11
5.3. Overview of Objectives and Endpoints	12
6. STUDY DESIGN	13
6.1. Scale and Duration.....	13
7. STATISTICAL CONSIDERATIONS	14
7.1. Endpoints	14
7.2. General Statistical Methods	14
7.2.1. Analysis Sets.....	14
7.2.2. Control of Systematic Error/Bias.....	15
7.2.3. Number of Subjects per Investigative Center	15
7.3. Data Analyses	15
8. VALIDATION	15
9. PROGRAMMING CONSIDERATIONS.....	15
9.1. Format of Output	15
9.2. Methods for Handling Missing Data	15
9.3. Rules and Definitions	16
9.4. Summarization of Site-Reported Serious and Non-Serious Adverse Events ..	16
10. BIBLIOGRAPHY.....	17

3.1. *Table of Figures*

Figure 4.1-1: WATCHMAN FLX Pro CT Study Design Overview 14

3.2. *Table of Tables*

Table 3.3-1: Overview of Objectives and Endpoints 13

4. Introduction

This statistical analysis plan (SAP) addresses the planned analyses for the clinical study entitled “A Pilot Study to Assess WATCHMAN FLX™ Pro Implants by Cardiac Computed Tomography, Magnetic Resonance Imaging and Transesophageal Echocardiography” (WATCHMAN FLX™ Pro CT). Approximately 25 consented subjects will be enrolled. Data for subjects receiving the WATCHMAN FLX Pro device will be collected over 12 months.

There is no formal statistical hypothesis for this observational, single-arm study.

5. Study Objectives and Endpoints

5.1. *Study Objectives*

The primary objective of this study is to measure device tissue coverage post-implantation of the WATCHMAN FLX™ Pro Left Atrial Appendage Closure (LAAC) Device (WATCHMAN FLX Pro) using the serial advanced imaging modalities of cardiac computed tomography (CT) and transesophageal echocardiography (TEE) and assess its relationship, if any, to clinical events.

5.2. *Study Endpoints*

Outcomes in WATCHMAN FLX Pro CT will be assessed on an intention-to-treat (ITT) basis and an implanted basis. The ITT analysis set includes all subjects who sign an Informed Consent Form approved by the Independent Ethics Committee (IEC) and are enrolled in the study, whether or not the WATCHMAN FLX Pro device is implanted. The implanted analysis set includes ITT subjects who are successfully implanted with the study device in the correct position.

Endpoints are listed below. Measurements will be collected peri- and post-procedure, predischarge, and at 14 days, 45 days, 3 months and 12 months after the implant procedure, unless specified otherwise.

The primary endpoint is device surface morphology (inclusive of tissue coverage) post implant procedure as assessed over time using the serial advanced imaging modalities of cardiac computed tomography (CT) and transesophageal echocardiography (TEE).

Additional endpoints will include the following:

- Endpoints adjudicated by an Independent Clinical Events Committee (CEC):
 - All-cause mortality (cardiovascular/unknown and non-cardiovascular)
 - Stroke (disabling and non-disabling; ischemic and hemorrhagic)
 - **Note 1:** For subjects diagnosed with a neurological event (e.g., stroke, transient ischemic attack [TIA]), mRS and NIHSS should be performed after the event. It is recommended that the subject be contacted regarding mRS assessment at 90±14

days following any suspected stroke; the simplified mRS questionnaire may be used for this follow-up assessment. It is recommended that imaging be performed after the event to screen for device related thrombus (DRT). If performed, imaging results should be sent to the core laboratory.

- Systemic embolism
- Bleeding: International Society on Thrombosis and Haemostasis (ISTH) major and non-major clinically significant
 - Procedural bleeding (≤ 7 days post-procedure)
 - Non-procedural bleeding (> 7 days post-procedure)
- Pericardial effusion/tamponade requiring pericardiocentesis or surgery
- Endpoints not adjudicated by an Independent Clinical Events Committee (CEC):
- Device success: defined as implantation of a WATCHMAN FLX Pro device without in-hospital mortality
- Assessments by serial imaging modalities (CT and TEE, optional cardiac magnetic resonance imaging [MRI]) at 14 days, 45 days, and 3 months (TEE optional at 3 months if there is no leak at 45 days). Data will be evaluated by an independent core lab.
 - Device seal at 45 days post index implant procedure (see **Note 2**)
 - Device-related thrombus (including hypoattenuated thickening [HAT] per CT analysis)
 - Device surface morphology (inclusive of tissue coverage) post implant procedure as assessed over time

Note 2: Results are classified as no leak, leak > 0 and ≤ 5 mm, or leak > 5 mm

Note 3: TEE should be performed at 12 months if the 3-month TEE assessment suggests a leak > 5 mm or the 3-month CT assessment suggests a leak > 3 mm; results must be sent to the core laboratory.

- 4D MRI flow analysis (if available) of the left atrium (LA) and LAA before (7 days prior to the index procedure) and serially after device implant (at 14 days, 45 days, and 3 months); data will be evaluated by an independent core lab
- Changes compared to baseline in measures of biochemical markers including coagulation, platelet and endothelial activation and inflammation over time post implant procedure (at 14 days, 45 days, and 3 months); correlations with morphological findings from imaging assessment of the device surface will be examined

5.3. *Overview of Objectives and Endpoints*

Table 5.3-1 provides an overview of the aforementioned study objectives and endpoints and a rationale for the specific endpoints.

Table 5.3-1: Overview of Objectives and Endpoints

Objective	Endpoint	Rationale for Endpoint
Evaluate safety of the implant and the procedure	Safety measures peri- and post-procedure and at 14 days, 45 days, 3 months, and 12 months post index procedure	Safety assessments per society guidelines.
Evaluate effectiveness of the implant	Implant performance and other effectiveness measures peri- and post-procedure and at 14 days, 45 days, 3 months, and 12 months (if needed) post index procedure, including core laboratory review of serial imaging post implant	Effectiveness assessments per society guidelines ^{39,40} .

a: Includes computed tomography and transesophageal echocardiography and optional cardiac magnetic resonance imaging

6. Study Design

[figure not shown]
WATCHMAN FLX™ Pro CT is a prospective, single-arm, single-center, post-market investigation to assess device tissue coverage in subjects with non-valvular atrial fibrillation (AF) who receive the WATCHMAN FLX Pro device to reduce the risk of stroke. Serial advanced imaging modalities such as CT and TEE will be used. A core laboratory will independently assess select results.

6.1. Scale and Duration

Up to 25 subjects in whom placement of a WATCHMAN device is attempted will be enrolled in WATCHMAN FLX Pro CT in 1 investigational center in western Europe. Eligibility for the study is determined per standard of care. Any additional study specific testing to verify inclusion/exclusion criteria (see Section 10 below) must be done after the ICF is signed.

All subjects will be assessed at baseline and post-implant on the procedure day, at predischarge, and at 14 days, 45 days, 3 months, and 12 months post index procedure. Follow-up will include in-person clinical assessments at all time points except 12 months (in person [preferred] or by telephone). Follow-up imaging assessments will occur at 14 days, 45 days, and 3 months. Additional imaging may be done at 12 months if required based on imaging data obtained at earlier time points.

Subjects who are enrolled but not implanted with a WATCHMAN FLX Pro device will be followed for safety through 12 months after the initial attempted index procedure but will not undergo imaging assessments or evaluation of biochemical markers including measures of coagulation, platelet and endothelial activation and inflammation. **Figure 6.1-1** provides an overview of the study design.

[^] Subjects must sign the study ICF before any study-specific assessments can be carried out.

^{*} Subjects who provide informed consent are considered enrolled.

[†] Post-procedure/Pre-discharge

[‡] Visits are in-person through 3 months and in-person (preferred) or via telephone interview at 1 year.

Figure 6.1-1: WATCHMAN FLX Pro CT Study Design Overview

Eligibility for the study is determined per standard of care. Any additional study specific testing to verify inclusion/exclusion criteria must be done after the ICF is signed.

Abbreviations: CT=computed tomography; ICF=Informed Consent Form

Enrollment is expected to take minimally 5 months; therefore, the total study duration from first subject enrolled to last subject follow-up is estimated to be at least 17 months. The study duration for each subject is expected to be approximately 12 months.

7. Statistical Considerations

7.1. Endpoints

Procedural and post-procedure information will be collected as detailed in the clinical study schedule and will be summarized using descriptive statistics for continuous variables (e.g., mean, standard deviation, n, minimum, maximum) and frequency tables or proportions for discrete variables. The Kaplan-Meier product-limit method will be used to estimate rates for time-to-event endpoints. Adverse event and SAE rates will be reported.

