EC11.	Subject has had a myocardial infarction (MI) documented in the clinical record as either a non-ST elevation MI (NSTEMI) or as an ST-elevation MI (STEMI), with or without intervention, within 30 days prior to enrollment.
EC12.	Subject has a history of atrial septal repair or has an atrial septal defect/patent foramen ovale (ASD/PFO) device.
EC13.	Subject has a known contraindication to percutaneous catheterization procedure.
EC14.	Subject has a cardiac tumor.
EC15.	Subject has signs/symptoms of acute or chronic pericarditis.
EC16.	Subject has an active infection.
EC17.	There is evidence of tamponade physiology.
EC18.	Subject has New York Heart Association Class IV congestive heart failure at the time of enrollment.
EC19.	Subject is of childbearing potential and is, or plans to become, pregnant during the time of the study (method of assessment per study physician's discretion).
EC20.	Subject has a documented life expectancy of less than 6 months.

Abbreviations: AF=atrial fibrillation; EC=exclusion criterion; eGFR=estimated glomerular filtration rate; ISTH=International Society on Thrombosis and Haemostasis; LAA=left atrial appendage; MRI=magnetic resonance imaging; TEE=transesophageal echocardiography

9. Subject Accountability

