9.1. Point of Enrollment

A subject is considered enrolled in the study when the subject or the subject's legally authorized representative signs an ICF approved by the IEC. No study-specific tests, procedures, etc. can take place until the ICF is signed. A subject who is determined to not

meet study specific clinical eligibility criteria after signing consent will be considered a screen failure (see **Table 9.4-1**) and will not count towards the enrollment ceiling.

9.2. *Withdrawal*

All subjects enrolled in the clinical study (including those withdrawn from the clinical study) shall be accounted for and documented. If a subject withdraws from the clinical investigation the reason(s) shall be reported. Reasons for withdrawal include but are not limited to physician discretion, subject choice to withdraw consent, or death. Reasons for study exit will be captured in the secure electronic data capture (EDC) system. If such withdrawal is due to problems related to device safety or performance, the investigator shall ask for the subject's permission to follow his/her status/condition outside of the clinical study.

While all efforts will be made to minimize attrition, subjects may withdraw from the study at any time, with or without reason, and without prejudice to further treatment. Withdrawn subjects will not undergo any additional study follow-up, nor will they be replaced. The investigator may discontinue a subject from participation in the study if the investigator feels that the subject can no longer fully comply with the requirements of the study or if any of the study procedures are deemed potentially harmful to the subject. Data that have already been collected on withdrawn subjects will be retained and may be used for analysis unless local regulations apply. No new data will be collected after subject withdrawal.

All applicable case report forms up to the point of subject withdrawal and an "End of Study" form for the subject must be completed. If the withdrawal is due to investigator discretion, the investigator should follow-up with the subject per standard of care.

9.3. *Lost to Follow-Up*

All enrolled subjects will be followed for up to 12 months post-procedure.

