7.2. General Statistical Methods

All statistical analyses will be performed using the SAS System software, version 9.2 or later (Copyright[©] 2000 SAS Institute Inc., [name], USA. All rights reserved).

All statistical analyses will be conducted according to applicable Standard Operating Procedures, Work Instructions, and the study-specific statistical analysis plan.

Statistical models that account for censored data will be employed in appropriate circumstances (e.g., for time-to-event outcomes).

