9.3. Rules and Definitions

Binary event rates (proportions) will be calculated on a per subject basis.

The number of subjects included in the outcome rates will be based on subjects who have adequate follow-up (see Section 9.4) and/or have experienced any events.

For baseline categorical variables, “unknown” responses and missing values will not be counted in rate denominators.

The date of last follow-up will be the latest of the following dates for each subject: date of a major event with CEC adjudication, index procedure date, discharge date, and scheduled follow-up visit date.

Days to (event or last known status) = (event or status) date minus procedure date.

Length of hospital stay = discharge date minus procedure date.

In-hospital event rates are calculated as the proportion of subjects who experience the specified event from index procedure through day of discharge out of all subjects enrolled.

Out-of-hospital event rates are calculated as the proportion of subjects who experience the specified event from the day after discharge through the number of days as specified out of all subjects who were discharged following index procedure and have adequate follow-up or have experienced the event as specified.

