9.4. Summarization of Site-Reported Serious and Non-Serious Adverse Events

Site-reported subject-based event rates will be calculated at various time points based on all events reported by the site.

The calculation method will follow the table below and extend to other endpoints and time points (e.g., 1 year death) with the appropriate modifications to the numbers of days. For example, for 90 days, the event must have occurred within 90 days of procedure and the valid data point must be 60 days (early portion of window for the 90-day visit).

The following are the maximum days to event and number of days post-procedure that are adequate follow-up:

Follow-up Visit	Maximum Days to Event*	Days for Adequate Follow-up**
14 Days	14	11
45 Days	45	30
3 Months	90	60
1 Year	365	335

* - this is the target date for the follow-up visit except for the 1-year visit where this is the end of the visit window

** - this is the start of the visit window

All event rates will be calculated relative to the date of procedure (i.e., post-procedure).

10. Bibliography

1. WATCHMAN FLX Pro CT Protocol, 92929614 Rev/Ver C.

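### Kaplan-Meier is the named estimator for time-to-event rates with no provision for death as a competing event, so 12-month rates of non-fatal endpoints may be slightly overstated

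*SAP*

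**What the plan says.** **Estimator.** SAP 7.1 states: "The Kaplan-Meier product-limit method will be used to estimate rates for time-to-event endpoints". Protocol 11.1.2 has the same sentence. Neither document says which endpoints count as time-to-event.

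**Censoring.** SAP 7.2 adds only a general statement: "Statistical models that account for censored data will be employed in appropriate circumstances (e.g., for time-to-event outcomes". There is no rule for death before a non-fatal event. SAP 9.3 dates last follow-up as the latest of the procedure, the discharge, the scheduled visits and any CEC-adjudicated major event, and counts time from the procedure to the event or to last known status.

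**Endpoints.** SAP 5.2 lists stroke, systemic embolism, bleeding (procedural to day 7, non-procedural after that) and pericardial effusion or tamponade. Beside them stands all-cause mortality, split into cardiovascular/unknown and non-cardiovascular. Protocol 11.2.4 sets the 1-year cut-off at 365 days.

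**A second method.** SAP 9.3 also says: "Binary event rates (proportions) will be calculated on a per subject basis". On the denominator it says "The number of subjects included in the outcome rates will be based on subjects who have adequate follow-up", "and/or have experienced any events". SAP 9.4 sets this out for site-reported events and lets it "extend to other endpoints and time points (e.g., 1 year death"), requiring 335 days for the 1-year row. The documents do not say which method supplies the headline 12-month rates.

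**Deaths within a year.** Exclusion criterion EC20 (Protocol 8.3) reads "Subject has a documented life expectancy of less than 6 months", so a subject expected to live 6 to 12 months is eligible.

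**The concern.** Death prevents a later stroke, embolism or bleed. If deaths are censored, Kaplan-Meier removes the subject from the risk set at death and implicitly gives that subject the later event risk of the survivors. The result estimates the rate in a hypothetical cohort in which nobody dies. It is not the proportion of this cohort that had the event, which is what a reader of a descriptive safety table expects. Any error is always upward.

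The same fault would affect mortality by cause. If cardiovascular/unknown and non-cardiovascular death were each estimated by Kaplan-Meier, the two figures would sum to more than all-cause mortality.

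**Working it through.** The plan gives no expected event or death rate for this cohort, so there is no figure to reproduce. The mortality and event rates below are assumptions, shown over a range.

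**1. Is death censored?** Death is a CEC-adjudicated endpoint (SAP 5.2). Taking it to be a major event under SAP 9.3, a subject who dies on day 200 without a stroke has last status at day 200 and no stroke event. In a Kaplan-Meier analysis of stroke that is a censored observation. The SAP does not use the word censored here, but it offers no other rule.

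**2. Direction.** At each event time let d be the events and n the number at risk.

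- 1 − KM = Σ S_e(t−)·d/n, where S_e counts only the endpoint as failure.
- Aalen-Johansen = Σ S_all(t−)·d/n, where S_all counts the endpoint or death as failure.

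S_e is never below S_all, so 1 − KM is never below the cumulative incidence. It is above it as soon as one death precedes a later event.

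**3. Size under constant hazards.** Take a 12-month 1 − KM of 15.0% (assumed), so h_e = −ln(0.85) = 0.1625, and h_d = −ln(1 − mortality). Then CIF = h_e/(h_e + h_d) × [1 − exp(−(h_e + h_d))].

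| Assumed 12-month mortality | h_d | CIF | Excess of 15.0% (points) | Relative excess |
|---|---|---|---|---|
| 5% | 0.0513 | 0.7601 × 0.1925 = 14.6% | 0.4 | 2.5% |
| 10% | 0.1054 | 0.6067 × 0.2350 = 14.3% | 0.7 | 5.2% |
| 15% | 0.1625 | 0.5000 × 0.2775 = 13.9% | 1.1 | 8.1% |

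For lower rates the excess is smaller. At 10% mortality it is 0.25 points on a 5% rate and 0.50 points on a 10% rate.

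**4. Against sampling error at n = 50.** The standard error of a 15% rate is √(0.15 × 0.85/50) = 5.0 points; for 5% and 10% rates it is 3.1 and 4.2 points. One subject is 2 points.

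**5. Order of events, N = 50, no other censoring.**

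- Five deaths, all before five events: 1 − KM = 5/45 = 11.1%; cumulative incidence = 5/50 = 10.0%.
- Five deaths, all before two events: 2/45 = 4.4% against 2/50 = 4.0%.
- All events before all deaths: the two estimates are equal.

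The last case is why procedural bleeding (day 7 or earlier) and peri-procedural effusion are hardly affected.

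**6. Mortality by cause, if each part were estimated by Kaplan-Meier.** N = 50, three cardiovascular deaths, then two non-cardiovascular: 3/50 = 6.00% and 2/47 = 4.26%. The sum is 10.26%, against an all-cause rate of 5/50 = 10.00%.

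**7. Do the proportions avoid the problem?** Only in part. Under the general SAP 9.3 rule, a subject who dies event-free stays in the denominator if death counts as an event. The out-of-hospital rule in the same section is narrower: it keeps those with adequate follow-up or with the specified event itself. A subject who dies on day 200 without it has fewer than 335 days and drops out. With 50 discharged, five event-free deaths before the required day and five events, the rate becomes 5/45 = 11.1% instead of 5/50 = 10.0%.

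**The case against.** The strongest reply is that this hardly matters. The study is descriptive, with no hypothesis and at most 50 subjects. The excess in step 3 is about half a subject at most, and the mortality figures behind it are assumed. That stands, and it makes the point a minor one.

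Stronger readings are tempting, and the documents do not support them:

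- A reader might infer that the plan explicitly censors deaths, because Protocol 9.2 says: "Reasons for withdrawal include but are not limited to physician discretion, subject choice to withdraw consent, or death". That section is subject accountability and not an analysis rule. Censoring at death follows from the ordinary reading of SAP 9.3; it is not stated.
- A reader might infer that Kaplan-Meier keeps the dead at risk. It does not; it removes them and extrapolates from survivors.
- A reader might infer that every non-fatal endpoint is overstated by the same proportion. That holds only under constant hazards through day 365, and fails for events close to the procedure.
- A reader might infer that all reported 12-month rates will be Kaplan-Meier rates. SAP 9.3-9.4 also define proportions, including a 1-year row.
- A reader might infer that separate Kaplan-Meier curves are planned for the two categories of death. Neither document says so; that limb is conditional.

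It is also fair to say that death is already an adjudicated endpoint, so nothing is missing from data collection.

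**Conclusion.** The point holds as a minor matter of specification. Kaplan-Meier is the only estimator named for time-to-event endpoints, death is not provided for as a competing event, and the ordinary reading of the SAP censors it. The 12-month proportions with stroke, systemic embolism or non-procedural bleeding would then be overstated whenever a death precedes a later event, and never understated on this account. The 0.4 to 1.1 point excess on a reported 15.0% rests on constant hazards and on the assumed mortality and event rates. It is well below sampling error at n = 50 and does not threaten the study's conclusions. The case for acting is that the bias runs in one direction and is cheap to remove.

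**What to change.** In SAP 7.1 and Protocol 11.1.2:

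1. List the time-to-event endpoints.
2. Report stroke, systemic embolism, bleeding and effusion/tamponade as Aalen-Johansen cumulative incidence with death as the competing event.
3. Report cardiovascular/unknown and non-cardiovascular death as cumulative incidences, which then sum to all-cause mortality.
4. Keep Kaplan-Meier for all-cause mortality.
5. State whether these estimates or the SAP 9.3-9.4 proportions are the headline 12-month rates.

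In SAP 9.3, including the out-of-hospital rule, keep subjects who die event-free in the denominator as non-events.

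The cost is a few SAP sentences, the matching protocol wording and slight extra programming; deaths are already collected and adjudicated. The SAP needs revision in any case, since it cites protocol version C and 25 subjects while the current protocol allows 50, and SAP 7.3 provides for amendment before analysis. The one drawback is a slightly less direct comparison with earlier device studies, if those reported Kaplan-Meier rates.
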